### 7.2 Serious Adverse Event (SAE)

Any adverse event or adverse reaction that:

- a. results in death
- b. is life threatening
- c. requires hospitalisation or prolongation of existing hospitalisation
- d. results in persistent or significant disability or incapacity
- e. consists of a congenital anomaly or birth defect
- f. is otherwise considered medically significant by the investigator
- g. Important adverse events/ reactions that are not immediately life-threatening or do not result in death or hospitalisation but may jeopardise the subject or may require intervention to prevent one of the other outcomes listed in the definition above.

### 7.3 Recording and reporting of Adverse Events

We do not anticipate that the use of the CE-marked TENS device will result in any serious adverse events. Participants will be given prior information regarding the reporting of adverse events and measure to take including instructions to contact the research team via a dedicated phone line.

Participants will be specifically queried regarding the following adverse events of special interest: any case of itching, skin breakdown, mild electrical burn, other skin allergies, or mild autonomic responses at each study visit, and reported related adverse events will be documented in an applicable adverse event form.

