#### 4.1 Study schedule

Participants will be asked to attend the CRF on 6 occasions.

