### Visit 4- Post Intervention Assessment Visit (end of the 6-week intervention):

Outcome assessments and procedure followed in Visit 1 will be repeated including questionnaires, treadmill protocol, blood sample collection and fitting of activPAL. The treadmill test will be by the investigators who are blinded to the participants group allocation. Participants will be given a prepaid envelope to return activPAL.

Post-Intervention Visit (70 mins)	Time (mins)	Responsible

a. Complete questionnaires:
 
 
1. Generic quality of life questionnaire (SF-36)
 
2. Intermittent Claudication Questionnaire (ICQ)
 
3. Visual Analogue Scale (VAS)
 
4. Geriatric Depression Scale (Short Form) (GDS-SF)
 
5. Pain Self-Efficacy Questionnaire (PSEQ)
 
6. Illness Perception Questionnaire (IPQ)
 
 
b. If participant is exiting the study at this point:
 
 
7. TENS feedback questionnaire
 
 
c. Questionnaire on adverse events of interest
	20	UA/JB
Treadmill protocol • MPQ (5 minutes post-treadmill protocol)	20	
Fitting of ActivPAL to participants and instruction for use	20	
Taking of blood sample	10	

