## 7.0 ADVERSE EVENTS

### 7.1 Definitions of adverse events

**Adverse Event (AE)** – Any untoward medical occurrence in a subject to whom a medicinal device has been administered, including occurrences which are not necessarily caused by or related to that product.

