### **8.5 Safety analysis**

The safety data (adverse events)- both numbers of subjects and events – will be summarised by randomised group and overall using descriptive statistics. No formal statistical tests comparing the randomised groups will be pre-specified.

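### The adverse event recording rule is narrower than the protocol's own definition and its safety summary, and the query promised for every visit is itemised only at Visit 4

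*Protocol*

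**What the plan says.** Protocol 7.1 takes in any untoward occurrence, "including occurrences which are not necessarily caused by or related to that product". Section 7.2 builds the serious category from any adverse event or reaction and sets no condition on relatedness.

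Section 7.3 describes two routes by which events reach the team. Participants receive "instructions to contact the research team via a dedicated phone line". They are also asked about a short list of special-interest events: itching, skin breakdown, mild electrical burn, other skin allergies and "mild autonomic responses at each study visit". The sentence ends with the only recording rule in section 7: "reported related adverse events will be documented in an applicable adverse event form".

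Section 4.1 states that "Participants will be asked to attend the CRF on 6 occasions". In the Study Schedule and in the visit tables of 4.1, the item "Questionnaire on adverse events of interest" appears under Visit 4.

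Protocol 8.5 summarises adverse events by arm and overall, "both numbers of subjects and events". The safety paragraph of the SAP repeats this, and SAP Table 2 has a row for the adverse event rate. None of the three is limited to related or listed events. Objective 2 (Protocol 2.2) speaks of specified adverse events, and Protocol 4.2.1 of defined ones.

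**The concern.** The form that feeds the safety table appears to collect a smaller set of events than the table claims to report. That matters in this trial because the interventions promote walking. Participants are advised to use the device before or during a challenging walk each day, the education arms set walking goals, and the treadmill tests run until claudication can no longer be tolerated. A fall, a muscle injury or exertional chest discomfort is outside the skin and autonomic list, and staff could regard it as unrelated to a TENS unit. Education is one of the two randomised factors, yet the list contains nothing specific to it.

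Safety is part of Research Question 1. A reader of the final report would take the by-arm table to cover adverse events as 7.1 defines them, and a definitive trial could plan its safety monitoring on that basis.

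**Working it through.** No plan figure needs reproducing and no formula applies. The check sets the passages side by side.

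**Step 1. Scope of events in each place.**

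| Place | Events covered |
|---|---|
| Protocol 7.1 | Any, related or not |
| Protocol 7.2 | Serious ones among any adverse event or reaction |
| Protocol 2.2 (objective 2) and 4.2.1; SAP objectives and outcomes | Specified or defined events |
| Protocol 7.3, query | The listed skin and mild autonomic effects |
| Protocol 7.3, recording | Reported events that are related |
| Protocol 8.5; SAP safety analysis; SAP Table 2 | Adverse events, no restriction |

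**Step 2. What *related* could mean.** It may mean related to the device, or relating to the special-interest list earlier in the same sentence. Both readings are narrower than 7.1, so the mismatch with 8.5 does not depend on which is chosen.

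**Step 3. One event followed through the text.** Suppose a participant falls on a planned walk in week 3, is not admitted to hospital, and telephones the team. Under 7.1 this is an adverse event. Under 7.2 it is not serious unless the investigator considers it medically significant or it meets another listed criterion. It is not on the 7.3 list. Under the 7.3 recording rule it is documented if it counts as related, and the text is silent if it does not. Under 8.5 it belongs in the table. Whether it is counted therefore rests on a decision that the protocol neither describes nor assigns to anyone.

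**Step 4. When the query is scheduled.**

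| Visit | Timing | Questionnaire itemised |
|---|---|---|
| 1, 2 | Before randomisation | No |
| 3 | Device issued | No |
| 4 | End of six weeks | Yes |
| 5 | Three months post-intervention, early recruits only | No |
| 6 | Focus group | No |

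That is 1 of 6 visits, or 1 of the 3 visits after device issue. The Visit 5 narrative says that the procedures of Visits 1 and 4, questionnaires included, are repeated, but the Visit 5 table lists seven questionnaires and this is not among them. The TENS feedback questionnaire given at exit does not clearly fill the gap: the SAP uses it for acceptability and blinding, and neither document says that it asks about adverse events.

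**Step 5. Sources of reports by arm.** The Visit 4 questionnaire and the phone line serve all four arms. The three 2-weekly follow-up calls go only to the two education arms. Those arms are one with active and one with placebo TENS, so extra contact is balanced across the TENS comparison and unbalanced across the education comparison.

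**The case against.** The strongest reply is that targeted collection was intended. Objective 2 covers specified events, 7.3 specifies them, the device is CE-marked and described as low risk, and the safety analysis is descriptive with no formal tests. On that view Objective 2 can be met as written and only wording is loose. The point about Objective 2 stands. It does not rescue 7.1, 8.5 or the SAP, none of which states the limited scope, and it leaves a table headed adverse events that contains something narrower.

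The scheduling gap is also smaller than one visit in six suggests. Visits 1 to 3 precede home use, Visit 4 closes the treatment period for everyone, and Visit 5 is for those recruited in the first eight months. That stands too. What remains is a conflict between 7.3 and the Visit 5 narrative on one side and the tables that staff would follow on the other.

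Three stronger readings are tempting, and the documents do not support them:

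- A reader might infer that every unrelated event is lost. Section 7.3 never says that only related events are recorded and describes no step in which relatedness is judged before recording. Participants are told how to report adverse events generally, and section 10.3 requires serious adverse event forms to be kept, so serious events probably have a form even though section 7 gives no procedure for it.
- A reader might infer that the arm comparison is biased. For active against placebo TENS nothing in the text shows this: participants and the outcome assessor are blinded to TENS type, and the calls fall equally on both. For education, unequal contact is a reason for caution about spontaneous reports. The calls are described as covering progress, barriers and goals, not adverse events, so bias is possible but not shown.
- A reader might size the problem by the confidence limit for zero events. With 40 per TENS type (2 arms × 20) the exact upper 95% limit is 1 − 0.025^(1/40) = 0.088. That reflects the sample size, would be the same after the fix, and does not measure this defect.

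**Conclusion.** The point holds as an inconsistency in the current text. The recording rule is narrower than the definition in 7.1 and than the summary in 8.5 and the SAP, under either meaning of *related*. Followed literally, the by-arm table would omit non-serious events not classed as related. Separately, the query promised for every visit is itemised at one of the three visits after device issue, and Visit 5 contradicts itself.

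The number of events affected cannot be estimated, because the documents give no event rates. The conclusion assumes that staff work from 7.3 and the visit tables as written, and that no recording procedure outside these documents widens them. Importance is moderate: it should be corrected because safety is one of the trial's stated questions, but the analysis is descriptive and the Visit 4 query already reaches all arms at the end of treatment.

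**What to change.** - **Protocol 7.3:** document every reported adverse event, related or not, with relatedness and seriousness as fields on the form.
- **Study Schedule and 4.1:** itemise the adverse event questionnaire at Visit 5 as well as Visit 4, so that the tables agree with 7.3 and with the Visit 5 narrative. Add one open question for unlisted events at both visits. Without it the questionnaire cannot pick up the walking and education harms at issue.
- **Protocol 8.5 and SAP safety analysis, with SAP Table 2:** tabulate all adverse events, related events and serious events by arm. Show events solicited at Visit 4 separately from spontaneous reports, because only the education arms receive follow-up calls.

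The cost is a few lines of protocol and SAP text, a few minutes per visit and a few more adverse event forms. Sample size and the efficacy analysis are unaffected.

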## 8. STATISTICS AND DATA ANALYSIS

### 8.1 Statistical analysis plan

The Robertson Centre for Biostatistics, part of the Glasgow Clinical Trials Unit, a fully registered UK CRN Clinical Trials Unit, will manage trial data.

Statistical analysis will be conducted by the Study Statistician from the Institute for Applied Health Research, Glasgow Caledonian University who is blinded to group allocation. The activPAL data will be downloaded and data input quality inspected visually and with diary information prior to statistical analysis. A detailed analysis plan will be prepared by the statistician and agreed with the Project Management Group and Trial Steering Committee.

Descriptive statistics will be used to characterize the groups at baseline and to present the feasibility outcomes. Outcomes related to experience and perception via focused group will be analysis by framework analysis. Comparisons will be undertaken to investigate the feasibility of studying the proposed outcomes for definitive trial and to calculate estimates for the likely effect sizes and 95% confidence intervals, even though determining differences in clinical outcomes is not the primary purpose of this feasibility trial. Inferential analysis will be implemented using the principles of intention-to-treat. The flow of participants through each stage of the trial will be presented in a CONSORT diagram.

### 8.2 Feasibility and acceptability analysis

To determine the feasibility of conducting a definitive trial, descriptive statistics will be used to report the number and proportion of participants who meet the inclusion criteria, who consented to participating, and who dropped out during the trial. Also descriptive analysis will report compliance with intervention by recording participants attendance to education session, follow up calls, attendance to TENS training session, (rate of use of TENS) rate of outcome measure completion, and total accelerometer wear time. Specifically, the TENS log (questionnaire) as well as inbuilt record of TENS device usage will both be used to analyse patients utilisation of TENS. Acceptability of TENS will be obtained by TENS feedback questionnaire

Further exploration will be carried out to determine factors that impact on propensity to participate looking at the difference in characteristics between participants and non-participants. If less than 10% of the individuals with PAD/IC in the clinic are eligible to participate, or if less than 10% of eligible patients agreed to participate, then the eligibility criteria and recruitment strategy will be adjusted prior to conducting a definitive trial. Adjustment of the recruitment strategy in a definitive trial will be made comparing the difference in the baseline characteristics between participants and non-participants. Similarly, association between participants' baseline characteristics and trial outcome will also inform decision on adjustment of recruitment strategy and stratification factors in the definitive trial. Data collection for the definitive trial will be adjusted based on the information related to type, quantity of missing data, and the mechanisms by which these data are missing.

The transcripts from the focus group discussions will be analysed using framework analysis. The data gathered from the exit interview will form part of acceptability analysis and be used to adapt the intervention to enhance its acceptability in a definitive trial.

### **8.3 Primary efficacy analysis**

Differences in the change in ACD will be analysed and effect scores calculated using Chi-squared tests, Mann-Whitney U or Wilcoxon signed-rank tests as applicable for between and within-group comparisons and log-rank method for pooled samples or sub-strata. Baseline participants' variability will be controlled for using the analysis of co-variance.

### **8.4 Secondary efficacy analysis**

Differences in the changes in activPAL outcomes, ICD, SF-36 and ICQ scores, MPQ score, IPQ, GDS-SF, PSEQ, and Biomarkers will also be analysed and effect scores calculated using Chi-squared tests, Mann-Whitney U or Wilcoxon signed-rank tests as applicable for between and within-group comparisons and log-rank method for pooled samples.

### **8.5 Safety analysis**

The safety data (adverse events)- both numbers of subjects and events – will be summarised by randomised group and overall using descriptive statistics. No formal statistical tests comparing the randomised groups will be pre-specified.

### **8.6 Software for statistical analysis**

The statistical software to be used is either SAS 9.2 for Windows, Cary, NC, USA or SPSS Version 22

### **8.7 Sample size**

For the primary outcome measure, at 80% power and a two-tailed 5% significance level, 16 participants per group will allow detection of an effect size of 1.0 standard deviations of ACD in active TENS group compared to placebo control. Attrition rates in our previous pilot studies ranged from 7.1% to 10% . We will recruit 20 participants in each group, allowing for 20% attrition, and therefore aim to recruit 80 patients. If this effect size were applied to our separate pilot studies, this would provide the ability to detect a change of 169m (TENS) or 322m (SEDRIC) in our primary outcome measure of ACD. Indeed, in these studies, a sample size of 20 per group (TENS) and 14 per intervention group (SEDRIC) was sufficient to detect a significant difference in this outcome measure.

### **8.8 Management and delivery**

Data analysis will be implemented by the trial statistician blinded to the group allocations. All statistical analyses will be conducted according to a pre-specified Statistical Analysis Plan.

## **9.0 STUDY CLOSURE / DEFINITION OF END OF TRIAL**

The study will end when the steering committee agrees that one or more of the following situations applies:

- Last patient last study visit

## 10. DATA HANDLING

### 10.1 Randomisation

A central randomisation facility (interactive web response system, IWRS) will allocate the randomised therapy per patient. The IWRS, based at the Data Centre, will be available by email.

### 10.2 Case Report Forms / Electronic Data Record

An electronic case report form (e-CRF) will be used to collect study data. The e-CRF will be developed by the study Data Centre at the Robertson Centre for Biostatistics, University of Glasgow and access to the e-CRF will be restricted, with only authorised site-specific personnel able to make entries or amendments to the patients' data. It is the responsibility of the research team to ensure completion and to review and approve all data captured in the e-CRF.

All data handling procedures will be detailed in a Study Specific Data Management Plan. Data will be validated at the point of entry into the e-CRF and at regular intervals during the study. Data discrepancies will be flagged to the study site and any data changes will be recorded in order to maintain a complete audit trail (reason for change, date change made, who made change).

### 10.3 Record Retention

To enable evaluations and/or audits from regulatory authorities, the investigators agree to keep records, including the identity of all participating subjects (sufficient information to link records), all original signed informed consent forms, serious adverse event forms, source documents, and detailed records of treatment disposition in accordance with ICH GCP, local regulations, or as specified in the Clinical Study Agreement, whichever is longer. Data will be retained at the Data Centre for a minimum of 5 years.

## 11.0 TRIAL MANAGEMENT

This research will fall under the auspices of the clinical governance structure of Glasgow Caledonian University (GCU) and NHS GGC Clinical research facility. The project is sponsored by GCU and the GCU Research and Development Office will have responsibility for oversight, including audit of adherence to protocol and research governance Standard Operating Procedures

### 11.1 Routine management of trial: Trial Management Group

The trial will be coordinated from Glasgow Caledonian University by the Trial Management Group. This will consist of the co-applicants, CRF research nurse, Robertson Centre for Biostatistics, and Glasgow Clinical Trial Unit. The trial Management Group will be responsible for the overall management and completion of the project to timescales. The role of the group is to monitor all aspects of the conduct and progress of the trial, ensure that the protocol is adhered to and take appropriate action to safeguard participants and the quality of the trial itself. The group will meet bimonthly mainly via telephone conferences.

### 11.2 Trial steering committee (TSC)

The Steering committee will utilise the strengths of diverse experts, including NHS services users. This will help ensure that the research is relevant and accessible to a diverse audience. The committee will have an independent chair ([name]). Specifically, the committee will advise on the suitability of the interventions for the population group and design and participate in dissemination activities. The group members will consist of: the chief investigators; Co-investigator

([name]); 2 patient representatives; an expert in patient education interventions and physical activity behaviour change; and an NHS management representative. The steering group will meet four times spread throughout the study and aims to provide advice from a broad perspective.

### **13. PROTOCOL AMENDMENTS**

Any change in the study protocol will require an amendment. Any proposed protocol amendments will be initiated by the CIs following discussion with the TSC and any required amendment forms will be submitted to the ethics committee, funder, sponsor and NHS GGC R&D for approval as appropriate to their role. The CIs and the TSC will liaise with study sponsor to determine whether an amendment is non-substantial or substantial. All amended versions of the protocol will be signed by the CI and Sponsor representative.

### **14. ETHICAL CONSIDERATIONS**

#### **14.1 Ethical conduct of the study**

The study will be carried out in accordance with the World Medical Association Declaration of Helsinki (1964) and its revisions (Tokyo [1975], Venice [1983], Hong Kong [1989], South Africa [1996] and Edinburgh [2000]). Favourable ethical opinion will be sought from an appropriate REC before patients are entered into this clinical trial. Patients will only be allowed to enter the study once they have provided written informed consent. The CI will be responsible for updating the Ethics committee of any new information related to the study.

#### **14.2 Informed consent**

Written informed consent shall be obtained from each trial participant. The Research Nurse will explain the exact nature of the study in writing, provision of patient information sheet, and verbally and will be responsible for consenting the participants. Trial participants will be informed that they are free to withdraw their consent from the study or study treatment at any time.

### **15. INSURANCE AND INDEMNITY**

NHS indemnity is provided under the Clinical Negligence and Other Risks Indemnity Scheme (CNORIS), and the Glasgow Caledonian University Indemnity insurance

### **16. FUNDING**

The trial is funded by CSO, grant award number TCS/16/55 (10 January 2017).

### **17. ANNUAL REPORTS**

An annual progress report will be submitted to the funder (CSO), the first being submitted 6 months from the date that all trial related approvals are in place. Annual reports will be submitted to the ethics committee and sponsor with the first submitted one year after the date that all trial related approvals are in place.

Recruitment data will, on a monthly basis, be uploaded to the UKCRN Portfolio database (and agreed successor to the database) through the mechanisms provided for the purpose, as part of CSO requirement. Also, updated information on the outputs from the project shall be uploaded through the e-VAL system, which is now accessed through the ResearchFish website - <https://www.researchfish.com/>. A final project report and other information and actions as required by CSO as part of the project completion will be available and completed to the satisfaction of CSO by the

end of the funding period. Copies of all publications originating from this trial shall be provided to CSO.

The Chief Investigators and Project Management Group will produce all reports. All statistical reports will be produced by the Study Statistician from the Institute for Applied Health Research, Glasgow Caledonian University.

